#### 6.2 Dose Rationale

The starting dose for this dose-escalation study was selected on the basis of the results of the 28-day toxicity studies in the rat and non-human primate (Cynomolgus), which indicated a NOAEL at 1000 mg/kg/day in rats and 20 mg/kg/day in non-human primates.

The Human Equivalent Dose (HED) would be 161 mg/kg and 6.45 mg/kg, calculated from NOAEL in rat and Cynomolgus (28-day toxicity studies) respectively, according to US Food and Drug Administration (FDA) Guidance for Industry [7], equivalent to 11.2 g and 451 mg for a 70 kg subject.

Considering the lowest of these HED values and a minimum safety margin of 10 as recommended by the FDA guidance above, a starting dose of 0.645 mg/kg was considered (ie, 45 mg for a 70 kg subject). This dose corresponds to the lowest estimate of the potential efficacious dose. In order to initiate this study at a dose lower than a potentially efficacious dose, the starting dose is to be 10 mg for a 70 kg subject.

The dose levels will be reviewed and can be altered based on emerging data. Dose escalation will only occur if the criteria listed in Section 8.2.1 is not met. If this criteria is met, or if it is deemed necessary, the dose selected for the subsequent cohort may be lower than the last. Dose escalation between cohorts will be limited to a maximal 5-fold increase for the first 3 cohorts and a maximal 3-fold increase thereafter, depending on safety and tolerability data and predicted exposure (both  $C_{max}$  and AUC). If mild or moderate adverse events (AEs) occur at a particular dose level, that dose level may be repeated, with the aim of further exploring the relationship between dose/exposure and AEs. If, in the judgement of the safety review committee (SRC), it would not be reasonable to expose more subjects to the level of discomfort experienced by those who have already received the dose, the next scheduled dose may be reduced. The reduction may be either to one of the dose levels that has already been given, or to an intermediate level that has not previously been given; in either case, the aim is to learn more about the relationship between AEs and dose (or plasma concentration) of DNDI-0690.

The exposure caps listed in Section 8.2.1 would allow for the predicted efficacious dose to be slightly exceeded. This is considered reasonable as the efficacious dose cannot be accurately confirmed at this stage, to allow the evaluation of the safety and PK of DNDI-0690 slightly beyond the predicted margin, see Table 2.

At high doses in non-clinical studies the bioavailability of DNDI-0690 decreased due to low solubility, hence lower absorption at high doses in preclinical species. In humans, DNDI-0690 absorption is also expected to decrease with dose, and DNDI-0690 is expected to show sub-proportional exposure increases at least at the higher dose levels.

There is no data on interactions with food once DNDI-0690 is administered in humans. Healthy subjects enrolled into Cohorts 1 to 6 and 8 in this study will therefore receive DNDI-0690 in the morning, after a fasting period of at least 10 h. Cohort 7 will include dosing after a high-fat breakfast (provided at least 30 min before dosing), to allow for a clinical assessment of interaction with food.

DNDI-0690 is a Biopharmaceutics Classification System (BCS) class II drug with poor aqueous solubility and good bioavailability. The drug is poorly soluble in gastrointestinal (GI) fluid, leading to saturation of the dissolution process. At some point, no more drug can dissolve into the GI fluid to be available for absorption. This could explain a plateau in drug exposure where increasing the dose is not proportionally increasing the exposure. Dissolution of active product ingredient in fed state simulated intestinal fluid (FeSSIF) media (pH 5.0), mimicking the fed condition, shows an increased dissolution up to 0.011 mg/mL after 4 h while fasted state simulated intestinal fluid (FaSSIF) media (pH 6.5), mimicking fasted condition, allows dissolution to reach 0.003 mg/mL [8]. The dose selected for the fed cohort will be approximately 3 times lower than the maximum dose shown to be well tolerated in the fasted state.

Exploring the dosing of DNDI-0690 in fed state will provide the following information:

- Firstly, dosing in fed state could potentially increase the absorption of the drug and thus could result in increased overall exposure, compared to fasted conditions, in order to reach the predicted exposure required for efficacy.
- Secondly, because the drug is predicted to have a relatively short half-life, this may result in the need for a BID dosing in the future MAD study, and consequently dosing of volunteers in a non-fasted state (afternoon administration).

Knowledge of the effect of food on both exposure and tolerability of DNDI-0690 will support the design of the next clinical study by ensuring a better prediction of exposure and consequently better safety monitoring.

Based on the predicted human PK parameters and considering the minimal unbound concentrations at steady state ( $C_{ss,min,u}$ ) needed for efficacy in the mouse and hamster leishmaniasis models, the human doses were calculated (standard clinical PK equations [6]) and  $k_{abs}$ >> $k_{el}$ ) to reach the same  $C_{ss,min,u}$  as in mouse (worst case) and hamster (best case). The resulting doses suggest that efficacy in humans may be achieved between 40 mg (based on hamster) and 110 mg/day (based on mouse) for a 50 kg patient with VL, equivalent to 56 mg and 154 mg/day for a 70 kg body weight subject. The underlying exposures at these doses are summarized in Table 2 below and put into context with projected exposures at starting dose and at highest dose.

Table 2 also serves as an indicator of the potential therapeutic index of DNDI-0690. For example, the projected exposure at the highest predicted efficacious dose based on total AUC provides a safety margin of 8-fold over the stopping rule exposure (essentially the same if  $C_{max}$  is considered).

DNDI-0690	Dose/subject (mg)	Est Human C max (μg/mL)	Est. Human AUC 0-24 (h*µg/mL)
First cohort dose	10	0.0958	0.913
Lowest Predicted efficacious dose	40ª (56 b )	0.383	3.65
Highest Predicted efficacious dose	110ª (154 b )	1.054	10.0
Example of a higher dose	500	4.790°	45.7°

#### Table 2Prediction of Exposure in Humans

a Dose is based on a 50 kg visceral leishmaniasis (VL)-patient

b Dose adjusted based on a 70 kg healthy volunteer

c Predicted AUC0-24 does not reach AUC0-24 based on stopping rule (100 h\* $\mu$ g/mL); Predicted Cmax does not reach Cmax defined as stopping rule (8.0  $\mu$ g/mL)

#### 6.3 **Population Rationale**

The purpose of this study is to show a difference between the applied conditions, and therefore it is an advantage to minimise variability.

Healthy male and females of non-childbearing potential volunteers will be included in the trial. As no information of reproductive toxicity in female subjects is available to date, women of childbearing potential (WOCBP) will be excluded from participating in the study. As women are part of the VL patient population, it is important for the development program to confirm if the exposure and the tolerability of DNDI-0690 in healthy women are no different from those in healthy men. Following completion of this study if they are confirmed as similar, this would support the inclusion of male and female subjects in the future studies and will help to ensure a better prediction of exposure and consequently better safety monitoring.

In order to facilitate recruitment of a sufficient number of WONCBP (which includes post-menopausal women) the age range for females enrolled in the trial will be 18 to 60 years.

In order to avoid any interaction with other medication, no prescribed or over-the-counter drug or vitamins/herbal remedies (eg St. John's Wort and others which are known to interfere with the CYP3A4 and P-gp metabolic pathways) or hormone replacement therapy (HRT) or co-medication will be allowed except up to 4 g of paracetamol in 24 h and those deemed necessary by the Investigator to treat AEs, see also Section 9.3. Based on observations in non-clinical studies, a parallel-group design is considered adequate for this study.

Subjects included will be male in the age group 18 to 55 or women of non-childbearing potential (WONCBP), in the age group 18 to 60 years, of normal weight, non-smokers and have no history of alcohol or drug abuse. The latter criteria are proposed to avoid interaction on drug metabolism and to avoid non-compliance as per European Medicines Agency (EMA) guidance.

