## 6 Rationale

#### 6.1 Study Rationale

DNDI-0690 is under development for treatment of Leishmaniasis. The present protocol constitutes a FIH study and all applicable precautions to ensure the safety of the subjects participating in the study will be taken.

In this trial, first data of PK and safety of single ascending oral doses of DNDI-0690 in humans will be assessed to evaluate further development of this compound.

DNDI-0690 is expected to have a relatively short half-life in humans (7.4 h) [2]. This may result in the need for twice a day (BID) dosing in the future multiple ascending dose (MAD) study, and consequently dosing of subjects in a non-fasted state. Knowledge of the effect of food on both exposure and tolerability of DNDI-0690 will support the design of the next clinical study by ensuring a better prediction of exposure and consequently better safety monitoring.

As women are part of the VL patient population, it is important for the development program to confirm if the exposure to DNDI-0690, the safety and tolerability of the drug are similar in women compared to men. If they are confirmed to be similar, this would support the inclusion of male and female subjects in the next clinical study and will help to ensure a better prediction of exposure and consequently better safety monitoring.

This trial is part of a clinical development program, and further trials may be conducted.

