#### 7.1.3 Exploratory Objectives

- To investigate any potential changes to renal toxicity markers in plasma and urine.
- To investigate the metabolite profile of DNDI-0690.
- To assess the effect of DNDI-0690 on Holter ECG parameters.
- To investigate the PK of DNDI-0690 after singles doses in the fed versus fasted state in healthy male subjects
- To investigate the PK of DNDI-0690 after single doses in healthy WONCBP versus healthy male subjects

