#### 7.2.3 Exploratory Endpoints

- Changes in clinical early renal toxicity markers in urine: alpha-glutathione Stransferase (α-GST), clusterin (CLU), Cystatin C (CysC), Kidney Injury Molecule-1 (KIM-1), neutrophil gelatinase-associated lipocalin (NGAL), osteopontin (OPN), albumin (ALB) and total protein (TPRO).
- Identification of DNDI-0690 metabolite profile (to be reported separately)
- Analysis of Holter extracted ECGs for the following parameters: RR, heart rate (HR), PR, QRS, QT, corrected QT interval by Fridericia's formula (QTcF), corrected QT interval by Bazett's formula (QTcB), ΔHR, ΔRR, ΔPR, ΔQRS, ΔQT, ΔQTcF and ΔQTcB.
- Comparison of the PK parameters AUC(0-t), AUC(0-inf) and Cmax of DNDI-0690 in the fed state versus fasted state in male subjects
- Comparison of the PK parameters AUC(0-t), AUC(0-inf) and Cmax of DNDI-0690 in WONCBP subjects versus male subjects

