#### 15.3 Pharmacokinetic Data Analysis

The plasma concentration data for DNDI-0690 provided by SGS Belgium will be analysed by Quotient Sciences, using Phoenix WinNonlin v8.0 or a more recent version (Certara USA, Inc., USA).

Plasma concentration data will be tabulated and plotted for each subject for whom DNDI-0690 concentrations are quantifiable. PK analysis of the concentration time data obtained will be performed using appropriate non-compartmental techniques to obtain estimates of the following PK parameters, where possible and applicable:

- **T**max: the elapsed time from dosing at which Cmax was apparent
- Cmax: the maximum observed concentration
- Cmax/D: the maximum observed concentration normalised for dose
- Cmax, norm: the maximum observed concentration normalised for dose and body weight
- AUC(0-24): area under the curve from 0 time to 24h
- AUC(0-t): area under the curve from 0 time to last measurable concentration
- AUC(0-t), norm: area under the curve from 0 time to last measurable concentration normalised for dose and body weight
- AUC(0-inf): area under the curve from 0 time extrapolated to infinity
- AUC(0-inf)/D: area under the curve from 0 time extrapolated to infinity normalised for dose
- **AUC**(0-inf), norm: area under the curve from 0 time extrapolated to infinity normalised for dose and body weight
- AUCt-inf: percentage of AUC(0-inf) extrapolated beyond last measured time point
- Points terminal: the number of points used to determine the elimination half-life
- T1/2: the apparent elimination half-life
- **C**I/F: apparent plasma clearance after oral administration
- Vz/F: apparent volume of distribution based on area for oral dose
- MRT: mean residence time
- lambda-z: the slope of the apparent elimination phase

The urine concentration data for DNDI0690 will be analysed for the following PK parameters:

- Ae: amount excreted
- **Fe:** fraction of dose excreted
- CLr: renal clearance

Amount excreted (Ae) and fraction excreted (Fe) will be calculated for 0-24 and 0-72 h.

Interim PK parameter estimations will be provided for dose escalation, as described in Section 8.2.

Further details of the PK data analysis will be included in the Reporting and Analysis Plan (RAP).

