#### 15.4 Statistical Data Analysis

Production of summary tables, figures and listings for this study will be performed by Quotient Sciences using the statistical package SAS (v9.4 or more recent version).

In general terms, categorical data (including TEAEs) will be presented using counts and percentages, while continuous variables will be presented using the mean, median, standard deviation, minimum and maximum. Additional statistics will be provided for PK-related data including coefficient of variation (CV%), geometric mean, geometric CV% and geometric n (ie the number of subjects with an observation that were included in the natural logarithmic transformation).

Descriptive summaries of all baseline characteristics and safety data (AEs, vital signs, ECGs and safety laboratory assessments) by all placebo dose subjects combined, all DNDI-0690 dosed subjects combined and for each dose level of DNDI-0690 will be provided (including changes from baseline as required).

Descriptive summaries for all PK data by dose level of DNDI-0690 will be provided.

In addition, dose proportionality will be assessed across dose groups (assuming same prandial status and same gender) using the power model. The power model will be applied separately to the ln(AUC) and ln(Cmax) values. A point estimate and its 90% confidence interval will be calculated for the population mean slope together with the acceptance range. Dose proportionality will be considered as statistically proven when the 90% confidence interval for the slope in completely contained in the acceptance range (1+ln(0.5)/ln(r)); 1+ln(2)/ln(r)) where r is the ratio highest/lowest dose. "In" denotes the natural logarithm.

Further statistical analyses of PK parameters  $AUC_{(0-t)}$ ,  $AUC_{(0-inf)}$  and  $C_{max}$  will be performed to examine the effect of food in males (comparing fed and fasted cohorts at same dose level) and the effect of gender (comparing male and female cohorts at same dose level). Populations for analysis will be determined for safety (safety analysis set) and PK (PK analysis set) data after database lock using the criteria defined in the RAP.

The safety population will be defined after database lock but prior to study unblinding; all other populations will be defined after database lock and unblinding when the relevant data are available.

Further details relating to the statistical analysis will be included in the study-specific RAP including the following:

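### The named female/male comparison cannot separate body weight from sex, and Sections 6.1 and 6.3 speak of confirming similarity where 6 versus 6 with no stated limit supports only an estimate

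*Protocol*

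**What the plan says.** **Purpose.** Section 6.3 says it is important to "confirm if the exposure and the tolerability of DNDI-0690 in healthy women are no different from those in healthy men", and continues that "if they are confirmed as similar, this would support the inclusion of male and female subjects in the future studies". Section 6.1 says the same of the next trial: "If they are confirmed to be similar, this would support the inclusion of male and female subjects in the next clinical study".

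**Objective and endpoint.** Section 7.1.3 lists the comparison as exploratory: "To investigate the PK of DNDI-0690 after single doses in healthy WONCBP versus healthy male subjects". Section 7.2.3 names AUC(0-t), AUC(0-inf) and Cmax "of DNDI-0690 in WONCBP subjects versus male subjects".

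**Analysis.** Section 15.4 applies the same three parameters to "the effect of gender (comparing male and female cohorts at same dose level"). It states no similarity limit for this comparison. For dose proportionality the same section does give an acceptance range and a rule for when the property counts as proven.

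**Parameters already available.** Section 15.3 derives Cmax,norm, "the maximum observed concentration normalised for dose and body weight", and AUC(0-inf),norm, "area under the curve from 0 time extrapolated to infinity normalised for dose and body weight", together with AUC(0-t),norm. Section 15.4 summarises all PK data descriptively by dose level but does not carry these parameters into the female/male comparison.

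**Size.** Section 15.1 reports no formal sample size calculation. Section 8.8.2 gives 1 + 5 = 6 subjects on active per cohort.

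**The concern.** Two separate things go wrong.

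First, the named comparison confounds sex with weight. Everyone in a cohort receives the same dose whatever their weight. The eligibility criteria limit BMI but not weight, and nothing matches the female cohort to the male one on weight. If the women are lighter, their exposure is expected to be higher even with no sex difference in the drug's kinetics. The result would be labelled an effect of gender. The next study needs to know which of the two it is: a weight effect applies to light men as well, and Section 5.3.1.2 takes 50 kg as the expected weight of adult patients.

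Second, the rationale promises more than the comparison can give. With no stated limit, the protocol does not say what result would count as similar. The obvious default is to see whether the interval includes 1, and with 6 per group that is a weak test. A sizeable difference could pass as similarity and be cited in support of enrolling both sexes.

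**Working it through.** The protocol states no CV, power or limit for this comparison, so there is no figure of its own to reproduce. The CVs and mean weights below are assumptions and are shown over a range.

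**Step 1. The protocol's weight scaling.** Section 6.2 converts the predicted efficacious doses from 50 kg to 70 kg:
- 40 × 70/50 = 56 mg
- 110 × 70/50 = 154 mg

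Both match the text. Table 2 assigns one Cmax (0.383 μg/mL) and one AUC (3.65 h·μg/mL) to 40 mg at 50 kg and to 56 mg at 70 kg. The protocol thus treats exposure as proportional to dose divided by weight.

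**Step 2. Ratio from weight alone.** At equal dose and with no sex effect, female/male ratio = male weight / female weight.

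| Assumed mean weights (women / men) | Ratio |
|---|---|
| 70 / 75 kg | 75/70 = 1.07 |
| 65 / 75 kg | 75/65 = 1.15 |
| 65 / 80 kg | 80/65 = 1.23 |
| 60 / 85 kg | 85/60 = 1.42 |

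**Step 3. Precision with 6 versus 6.** Two independent groups on the log scale, pooled t with 10 df:
- SD = √ln(1 + CV²)
- SE = SD × √(2/6)
- 90% half-width = 1.812 × SE

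| CV | SD | SE | Half-width | Ratio divided and multiplied by |
|---|---|---|---|---|
| 20% | 0.198 | 0.114 | 0.207 | 1.23 |
| 30% | 0.294 | 0.170 | 0.307 | 1.36 |
| 40% | 0.385 | 0.222 | 0.403 | 1.50 |

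**Step 4. How often weight alone would look like a sex effect.** Noncentral t with 10 df and noncentrality ln(ratio)/SE. At CV 30% and 65 versus 80 kg, noncentrality = ln(1.231)/0.1695 = 1.225. The 90% CI excludes 1 in 31% of trials, against 10% if there were no difference at all. With 65 versus 75 kg the figure is 20%.

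**Step 5. How often a real difference leaves 1 inside the interval.** For a true ratio of 1.5:
- CV 20%: noncentrality 3.55, interval includes 1 in 5% of trials
- CV 30%: noncentrality 2.39, 28%
- CV 40%: noncentrality 1.82, 48%

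**Step 6. Chance of showing similarity if the sexes are identical.** Probability that the 90% CI lies wholly inside the limits, by simulation. The limits are assumptions too.

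| Limits | CV 20% | CV 30% | CV 40% |
|---|---|---|---|
| 0.80 to 1.25 | 20% | 1.7% | 0.2% |
| 0.70 to 1.43 | 79% | 29% | 7% |
| 0.5 to 2 | 100% | 97% | 79% |

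The answer runs from almost never to almost always, according to two quantities the protocol does not give.

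**The case against.** **Flat-dose exposure is the right quantity for safety.** Dosing is flat, and the exposure caps in Section 8.2.1 are absolute. If women reach higher concentrations because they weigh less, that is still the exposure they have. This stands: the unadjusted ratio should remain the main result. The gap is only that no normalised ratio is named beside it.

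**Weight is already partly covered.** Cmax,norm and AUC(0-inf),norm are secondary endpoints in Section 7.2.2, all PK data are summarised and listed, and body weight is recorded at screening, Day -1 and 72 h. The analysis plan, which is not at hand, may add weight as a covariate. This stands in part. A weight difference would be visible, but the comparison fixed in Sections 7.2.3 and 15.4 would not adjust for it.

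**The weight scaling is a simple dose conversion, not an exposure model.** True, and the mean weights are assumed. The 1.23 illustrates the size and is not a prediction. Still, it is the only weight relation in the protocol, and Table 2 attaches exposures to it.

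**The operative text is modest.** The objective is to investigate, the endpoint is a comparison, no equivalence test is promised, and talk of confirming appears only in the rationale. This limits the consequence but leaves the rationale claiming more than the analysis delivers.

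**Stronger readings.** A reader might infer that similarity cannot be shown with 6 per group. The documents do not support that: it depends on the CV and the limit, and step 6 gives 97% for 0.5 to 2 at CV 30%. A reader might also infer that the decision to enrol women rests on this AUC and Cmax ratio alone. Section 6.1 names safety and tolerability as well, and says only that similarity would support inclusion.

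**Conclusion.** The point holds in two limited parts.

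The comparison named in Sections 7.2.3 and 15.4 cannot distinguish a weight effect from a sex effect, although the parameters that would help are already derived. On the protocol's linear scaling the spurious ratio is 1.23 for assumed means of 65 and 80 kg (1.07 to 1.42 over the range tried).

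The wording in Sections 6.1 and 6.3 is stronger than an exploratory, unsized comparison of 6 versus 6 without a similarity limit can bear. At assumed CVs of 30% to 40%, the absence of a detected difference would be compatible with a 1.5-fold true difference in 28% to 48% of trials. At CV 20% that figure falls to 5%, so the weight of this second part depends on a variability that the protocol does not state.

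Nothing in the protocol says that an interval including 1 will be taken as similarity. The risk is that nothing rules it out.

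**What to change.** 1. **Sections 7.2.3 and 15.4:** add AUC(0-t),norm, AUC(0-inf),norm and Cmax,norm to the female/male comparison as a supportive analysis. Keep the flat-dose ratio as the main, safety-relevant result and report the two side by side.
2. **Sections 6.1 and 6.3:** for exposure, replace confirming that women are similar to, or no different from, men with estimating the female/male ratio with its 90% CI. State that an interval including 1 is not by itself evidence of similarity.

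No new data, samples or subjects are needed. The cost is one extra analysis, an edit to four sections and a weaker stated claim.
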